#### 2. INTRODUCTION

This SAP provides the detailed methodology for summary and statistical analyses of the data collected in Study GBT440-042 for the final CSR after last subject last visit (LSLV). This document may modify the plans outlined in the protocol, however, any major modifications of the primary endpoint definition or its analysis will also be reflected in a protocol amendment. Statistical analyses will be performed using cleaned case report form (CRF) data as well as non-CRF data (i.e., blood samples data and banked biospecimens).

The administration of the study intervention was voluntarily paused by the Sponsor on 10 May 2024 due to the overall number of deaths observed in the study. The decision was made by the sponsor to terminate the study on 25 September 2024 and the LSLV was on 22 October 2024.

## 2.1. Modifications to the Analysis Plan Described in the Protocol

Not applicable.

## 2.2. Study Objectives and Endpoints

Туре	Objective	Endpoint
Primary	Primary	Primary
Efficacy	Characterize the effect of voxelotor and SOC (standard of care) compared to placebo and SOC on leg ulcer healing in participants ≥ 12 years of age with SCD by Week 12	The proportion of participants achieving resolution of the target ulcer(s), CCI  during the 12-week  Randomized Treatment Period. CCI
Secondary	Secondary	Secondary
Efficacy	Characterize the effect of voxelotor and SOC compared to placebo and SOC on secondary endpoints	
 
Time (in days) to resolution of target ulcer(s) up to Week 12
 
Change in total surface area(s) of target ulcer(s) at Week 12
 
Incidence of new ulcers by Week 12
 

Exploratory	Exploratory	Exploratory
Efficacy	Characterize the effect of voxelotor and SOC compared to placebo and SOC on exploratory endpoints	
 
Proportion of participants achieving resolution of target ulcer(s) by Week 24
 
Time (in days) to resolution of target ulcer(s) up to Week 24
 
Change from baseline in total surface area of target ulcer(s) over time up to Week 24
 

[figure not shown]
Туре	Objective	Endpoint
		Correlation between change in Hb and target ulcer(s) healing at Week 12 and Week 24  Correlation between change in hemolytic parameters (% reticulocytes, indirect bilirubin, LDH) and target ulcer(s) healing at Week 12 and Week 24  Health-related quality of life (HRQOL) using patient-reported outcome (PRO) measures, when available (pending translation and cultural validation requirements)  Change from baseline in PRO HRQOL measures: PROMIS-37 v2.0 Pediatric Profile/PROMIS-43 v2.1 at Week 12 and Week 24  Change from baseline in pain level linked to target ulcer(s) assessed by VAS at Week 12 and Week 24  Patient Global Impression of Change (PGI-C) score at Week 12 and Week 24  Clinician Global Impression of Change (CGI-C) score at Week 12 and Week 24
Safety	Assess the safety and tolerability of voxelotor compared to placebo	
 
AEs
 
Clinical laboratory tests
 
Physical examinations
 
Vital signs
 
Other clinical measures (eg. discontinuation due to AEs, dose reductions)
 

## 2.3. Study Design

This study is a Phase 3, multicenter, randomized, placebo-controlled study to evaluate the efficacy of voxelotor and SOC for the treatment of leg ulcers in participants with SCD. The study is divided into 5 study periods: Screening, Run-in, Randomized Treatment, Open-label Treatment, and Follow-up/End of Study (EOS).

The study will be conducted in approximately 80 eligible participants at approximately 20 global clinical trial sites. Participants in this study will have safety and efficacy assessments performed at the investigative clinic per the protocol Schedule of Assessments. The overall study design is illustrated in the Study Schema provided in Figure 1. Study Schema

Figure 1. Study Schema

Abbreviations: SOC, standard of care

\* Participants who have completed 12 weeks in the Open-label Treatment Period may continue to receive voxelotor as long as they continue to receive clinical benefit that outweighs risk as determined by the Investigator or until the participant has access to voxelotor from an alternative source (eg, through a clinical OLE study sponsored by Pfizer, commercialization of the product, or a managed access program). Participants who do not plan to continue to receive voxelotor from an alternative source should continue to the follow-up period after completing 12 weeks in the Open-label Treatment Period.

#### 2.3.1. Sample Size Determination

Approximately 80 participants will be enrolled in the study. Participants will be randomized in a 1:1 ratio to receive treatment with voxelotor 1500 mg or placebo for 12 weeks. The primary endpoint will be measured by the proportion of participants achieving resolution of the target ulcer(s).

during the 12-week Randomized Treatment Period. CCI

For the primary endpoint, the sample size of 80 participants (40 participants per treatment group) provides approximately 90% power to detect a 35% absolute difference between treatment groups (voxelotor 1500 mg + SOC versus placebo + SOC) in proportion of participants experiencing resolution of the target ulcer(s) by Week 12. Calculations were based on a two-sided alpha = 5% test of the difference in two binomial proportions (Normal approximation).

## 2.3.2. Treatment Group and Reporting Period for Analysis

In the study schematic in Figure 1. Study Schema, the study period and treatment groups to be included in the primary and open-label analysis.

Efficacy and Safety: Primary analysis (Randomized Treatment Period):

- Treatment groups:
  - Voxelotor: participants randomized to voxelotor.
  - Placebo: participants randomized to placebo.
- Reporting Period:
  - From Day 1 through Week 12 for subjects who either do not achieve confirmed reepithelialization or achieve it before or at Week 12 visit.
  - From Day 1 through Week 14 for subjects who have the initial skin reepithelialization confirmed at Week 12 and then the 14-week visit will be used to confirm resolution.

Day 1 is defined as the date of randomization. The last day (i.e. Week 12 visit or Week 14) of randomized treatment period is defined as the last day entered on the disposition page for end of randomized treatment period.

Efficacy: Open-label analysis (Open-Label Treatment Period):

- Treatment groups:
  - Voxelotor: participants randomized to voxelotor who received at least one dose of voxelotor.

- Delayed voxelotor: participants randomized to placebo during Randomized Treatment Period (through Week 12) and who received at least one dose of voxelotor on or after the Week 12 visit.
- Total: participants who received at least one dose of voxelotor.

## Reporting Period:

- After Week 12 (one day after Week 12 visit) through Week 24 for subjects who either
  do not achieve confirmed re-epithelialization or achieved it before or at Week 12
  visit.
- After Week 14 (one day after Week 14 visit) through Week 24 for subjects who have the initial skin re-epithelialization confirmed at Week 12 and then the 14-week visit will be used to confirm resolution.

Safety: Open-label analysis (Open-Label Treatment Extension Period which is combining the entire Open-Label Treatment Period and the Follow-up Period):

#### Treatment groups:

- Voxelotor: participants randomized to voxelotor and received at least one dose of voxelotor.
- Delayed voxelotor: participants randomized to placebo and who did not receive voxelotor during Randomized Treatment Period (through Week 12) and who received at least one dose of voxelotor on during the open-label period (or after the Week 12).
- Total: participants who received at least one dose of voxelotor.

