#### Reporting Period:

- After Week 12 (one day after Week 12 visit) through end of study for subjects who
  either do not achieve confirmed re-epithelialization or achieved it before or at Week
  12 visit.
- After Week 14 (one day after Week 14 visit) through end of study for subjects who
  have the initial skin re-epithelialization confirmed at Week 12 and then the 14-week
  visit will be used to confirm resolution.

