## 4. ANALYSIS SETS (POPULATIONS FOR ANALYSIS)

For purposes of analysis, two main analysis populations are defined for this study as below.

Population	Description
	All randomized participants according to the treatment group to
_	which they were randomized, regardless of the treatment received
	All randomized participants who received at least one dose of study drug, regardless of the group to which they were randomized

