#### 6. ANALYSES AND SUMMARIES

Analyses based on ITT participants will be grouped according to the treatment assigned at randomization and for Safety-Evaluable populations, participants will be grouped according to the actual study drug taken.

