#### 6.3. Exploratory Efficacy Endpoints

Endpoint: The proportion of participants achieving resolution of the target ulcer(s) by Week 24

Population: ITT population as described in Section 4.

Analysis: Descriptive statistics including the number of participants (N) and percentage (%) will be provided by Voxelotor and delayed Voxelotor groups.

Endpoint: Time (in days) to resolution of target ulcer(s) up to Week 24

Population: ITT population as described in Section 4.

Analysis: Number of participants (N) who achieved resolution of target ulcer, median, first quartile (Q1), third quartile (Q3), minimum, and maximum will be provided by Voxelotor and Delayed Voxelotor groups.

Endpoint: Change from Baseline in total surface area of target ulcer(s) over time up to Week 24

Population: ITT population as described in Section 4.

Analysis: Descriptive statistics including the number of participants (N), mean, standard deviation (SD), median, first quartile (Q1), third quartile (Q3), minimum, and maximum will be provided by Voxelotor and Delayed Voxelotor groups.

Endpoint: Correlation between change from Baseline in Hb and target ulcer(s) healing at Week 12 and Week 24.

Population: ITT Population as described in Section 4.

Analysis: The point biserial correlation  $r_{pb}$  will be provided as described in Section 5.2.4 by treatment groups.

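### SAP 2.3.2 sets different entry rules for the two open-label groups, so post-Week-12 safety denominators are not comparable, and three Week 24 ulcer displays labelled ITT use columns defined by dosing

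*SAP*

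**What the plan says.** **Entry to the open-label groups.** For safety, SAP 2.3.2 defines the Voxelotor group as "Voxelotor: participants randomized to voxelotor and received at least one dose of voxelotor", with no condition on when the dose was taken. Delayed voxelotor is the placebo arm, restricted to those who took voxelotor in the open-label period or after Week 12. Total is anyone with at least one voxelotor dose. The efficacy groups follow the same pattern: any voxelotor dose for the voxelotor arm, but placebo participants only if they are people "who received at least one dose of voxelotor on or after the Week 12 visit".

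**Period counted.** The open-label safety period runs "After Week 12 (one day after Week 12 visit) through end of study for subjects" in the usual case. It starts after Week 14 for those whose first re-epithelialisation is seen at Week 12.

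**Populations.** SAP 4 defines ITT as all randomised participants in the group to "which they were randomized, regardless of the treatment received". SAP 6 adds: "Analyses based on ITT participants will be grouped according to the treatment assigned at randomization". Safety analyses use the safety-evaluable population (SAP 6.6).

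**Week 24 ulcer displays.** SAP 6.3 and SAP Appendix 1 label resolution, time to resolution and surface area up to Week 24 as ITT. In SAP 6.3 the summaries use the two open-label groups. For resolution, for example, they "will be provided by Voxelotor and delayed Voxelotor groups".

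**Context.** SAP 2 reports: "The administration of the study intervention was voluntarily paused by the Sponsor on 10 May 2024". The reason it gives is the number of deaths in the study. Protocol 8.6 plans 40 per arm with 5% dropout by Week 12. Neither document gives an open-label group size.

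**The concern.** Take two participants who both leave at Week 5, one from each arm. Neither can contribute an event to a period that starts after Week 12. The voxelotor participant is still counted in the Voxelotor and Total denominators, and the placebo participant is counted in neither. The Voxelotor percentage is therefore diluted relative to Delayed voxelotor, which makes the arm with longer exposure look somewhat safer.

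The rule can also lose placebo-arm events from the tables. The on-treatment window in SAP 2.3.3 extends up to 28 days past the last dose. A placebo participant who stops at Week 11 and never starts open-label drug can have a treatment-emergent event after Week 12. That event falls outside the randomised reporting period, and the participant is not in Delayed voxelotor. The same event in the voxelotor arm would be tabulated.

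In a study paused because of deaths, post-Week-12 event percentages will be read closely.

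For Week 24 healing, the population label and the column definitions conflict. Read literally, a placebo participant with no open-label dose belongs to the ITT population but has no column.

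**Working it through.** The plan states no open-label denominator, so there is no figure of its own to reproduce.

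**Inputs.** 40 per arm (Protocol 8.6, SAP 2.3.1). 5% dropout by Week 12 (Protocol 8.6), used as a rough stand-in for d: 0.05 × 40 = 2 people per arm. Assumed: every voxelotor participant was dosed at least once; d is equal in both arms; 8 people with events per safety column; 18 resolvers per arm at Week 24.

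**Step 1: does another section repair the asymmetry?** SAP 4 requires one dose of study drug, SAP 6 groups safety by drug taken, and SAP 6.6 names the population and the period. None requires time at risk in the open-label period.

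**Step 2: general form.** Let r be the true risk among those with time in the period.
- Voxelotor: events = r × 40 × (1-d) and denominator = 40, so the percentage is r(1-d).
- Delayed voxelotor: events = r × 40 × (1-d) and denominator = 40 × (1-d), so the percentage is r.
- The ratio is 1-d.

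**Step 3: safety percentages.** n is the number per arm with no later risk time. Only the first row uses a planning figure from the documents; the others are assumptions.

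| n (d) | Voxelotor | Delayed voxelotor | Gap | Total as written | Total, one rule |
|---|---|---|---|---|---|
| 2 (5%) | 8/40 = 20.0% | 8/38 = 21.1% | 1.1 points | 16/78 = 20.5% | 16/76 = 21.1% |
| 4 (10%) | 8/40 = 20.0% | 8/36 = 22.2% | 2.2 points | 16/76 = 21.1% | 16/72 = 22.2% |
| 6 (15%) | 8/40 = 20.0% | 8/34 = 23.5% | 3.5 points | 16/74 = 21.6% | 16/68 = 23.5% |

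Check of the first row against Step 2: 21.05% × 0.95 = 20.0%.

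**Step 4: Week 24 resolution.** Both arms are truly 18/40 = 45.0%, and two placebo participants have no open-label dose.
- Both unresolved: 18/38 = 47.4%, or 2.4 points above the ITT value.
- Both resolved: 16/38 = 42.1%, or 2.9 points below it.

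**Step 5: the pause.** Study Day 84 is the randomisation date plus 83 days (SAP 2.3.3). 10 May 2024 minus 83 days is 17 February 2024, so anyone randomised later had not reached Day 84 when dosing stopped. That does not mean no later risk time. With the 28-day window, 10 May plus 28 days is 7 June, and 7 June minus 83 days is 16 March. A voxelotor participant randomised up to about then and dosed until the pause could still reach Day 84 on treatment.

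**The case against.** **Dropout is not d.** The 28-day window gives some early stoppers risk time after Week 12, and Protocol 3.2 keeps participants in follow-up to at least Week 12 after stopping treatment. This stands: 5% is a proxy only.

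**The period may be undefined for early leavers.** It starts the day after the Week 12 visit, so a person without that visit has no start date. True, but the groups are defined by dosing alone, and nothing removes that person from the denominator.

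**Delayed voxelotor may be only a column name for the placebo arm.** SAP 6 groups ITT analyses by randomised arm, and on that reading the three displays are ITT. A reader might infer that they are certainly not ITT. The documents do not settle that. They show a conflict, because SAP 2.3.2 defines the same term by dosing.

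**The direction of the Week 24 bias.** A reader might infer that the rule favours Delayed voxelotor. That holds only if the excluded participants were unresolved. Protocol 3.1, read literally, excepts those first re-epithelialised at Week 12 from open-label drug, so excluded participants may well have healed.

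**Time to resolution up to Week 24.** The statistics listed in SAP 6.3 could be read as covering resolvers only. SAP 5.2.3 already gives Kaplan-Meier as the general method, so this needs at most a clarifying sentence.

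**Small and descriptive.** At the planned dropout the safety gap is about one point. SAP 6.6.1 also lists SAEs and deaths. This limits the weight of the point but does not remove it.

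**Conclusion.** The safety entry rule is wrong as written. It conditions one arm on a later dose and the other on any dose, for a period in which only later events count. The Voxelotor percentage is understated by the factor 1-d relative to Delayed voxelotor. At the 5% proxy, with 8 assumed events per column, the gap is 1.1 points (20.0% against 21.1%). Larger gaps rest on assumed values of d. A reader might infer from the pause that d is large, or that deaths are being hidden. The documents support neither: they give no count of participants caught by the pause, and deaths and SAEs are listed individually.

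The Week 24 ulcer displays have a real conflict between population label and columns. Its effect can go either way (42.1% to 47.4% around 45.0% in the example, with two people excluded). Only these three displays name the open-label groups. The other Week 24 displays refer to treatment group and are not shown to be affected.

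The affected displays are descriptive, and the Week 12 primary and secondary analyses are untouched. The point is worth correcting because the change is cheap and the post-Week-12 safety tables will matter to readers.

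**What to change.** 1. **Open-label safety.** Apply one entry rule to Voxelotor, Delayed voxelotor and Total: at least one voxelotor dose in the open-label period. Keep the randomised-period tables at the Week 12/14 limit of SAP 2.3.2, so that unequal later follow-up does not enter the only controlled safety comparison. Tabulate post-Week-12 TEAEs, SAEs and deaths of participants with no open-label dose separately, by randomised arm.
2. **The three Week 24 ulcer displays.** Show all randomised participants by randomised arm. For resolution, count those who leave or die without confirmed resolution as not resolved, which extends SAP 5.3.1.
3. **Side point.** SAP 2.3.2 starts the efficacy open-label period "After Week 14 (one day after Week 14 visit) through Week 24 for subjects who have the initial skin re-epithelialization" at Week 12, and does likewise for safety. Protocol 3.1 excepts these participants from open-label drug, Protocol 5.1 gives it to all, and footnote u of Protocol Appendix 1 keeps them on assigned treatment for two more weeks. These passages must be reconciled so that it is clear when such participants enter the open-label columns.

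Cost: a few SAP sentences, minor reprogramming and one extra table, with no new data. The voxelotor open-label denominator becomes smaller. Participants who stopped shortly before Week 12 but still have some on-treatment time move from the Voxelotor column to the extra table.

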## 8.1. Analysis Populations

Two main analysis populations are defined for this study: the intent-to-treat (ITT) population and the safety-evaluable population.

The ITT population includes all randomized participants. For analyses based on this population, participants will be grouped according to the treatment assigned at randomization. This is the primary analysis population for efficacy, demographics, and baseline characteristics data.

The safety-evaluable population includes all participants who receive at least 1 dose of study drug. For analyses based on this population, participants will be grouped according to the actual study treatment received. This is the primary analysis population for safety and exposure data.

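### SAP 2.3.2 groups randomized-period safety by assigned arm, while SAP 6 and Protocol 8.1 group it by drug actually taken; its two open-label safety columns also need not sum to Total

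*SAP*

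**What the plan says.** SAP 2.3.2 opens with a block headed "Efficacy and Safety: Primary analysis (Randomized Treatment Period", so its groups apply to safety as well as efficacy. The groups are "Voxelotor: participants randomized to voxelotor" and "Placebo: participants randomized to placebo", that is, assigned arm.

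SAP 6 says that "for Safety-Evaluable populations, participants will be grouped according to the actual study drug taken". Protocol 8.1 says the same of the safety-evaluable population: "For analyses based on this population, participants will be grouped according to the actual study treatment received". SAP 4 defines that population as "All randomized participants who received at least one dose of study drug, regardless of the group to which they were randomized". SAP 2.1 lists no modification of the protocol's analysis plan. SAP 6.6 refers safety analyses to both Section 4 and Section 2.3.2 without saying which prevails.

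For open-label safety, SAP 2.3.2 has three columns. Voxelotor requires randomization to voxelotor and at least one voxelotor dose. Delayed voxelotor is restricted to "participants randomized to placebo and who did not receive voxelotor during Randomized Treatment Period (through Week 12", with a first dose in the open-label period. The third is "Total: participants who received at least one dose of voxelotor", with no condition on assigned arm or on timing. The open-label efficacy version of Delayed voxelotor has no exclusion for earlier voxelotor.

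**The concern.** The two randomized-period rules give the same answer for everyone who took the assigned drug, and different answers for anyone who did not. The plan foresees such participants. The exclusion in the Delayed voxelotor definition has work to do only if a placebo participant received voxelotor early, and Protocol 7.7 lists giving an incorrect study drug as a medication error.

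Two programmers following different sections could place the same participant in different arms of the placebo-controlled safety tables. In the open-label tables, such a participant's events could count in Total but in neither column beside it. SAP 2 records that dosing was paused because of the number of deaths in the study, so these tables will be read closely and one participant's placement can be noticed.

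**Working it through.** The plan states no figure to reproduce here. The check applies each rule literally to every combination of assigned arm and drug taken.

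| Assigned | Taken in randomized period | Voxelotor in open-label period | Randomized-period group, SAP 2.3.2 | Randomized-period group, SAP 6 / Protocol 8.1 | Open-label safety columns |
|---|---|---|---|---|---|
| Voxelotor | Voxelotor only | Yes or no | Voxelotor | Voxelotor | Voxelotor, Total |
| Placebo | Placebo only | Yes | Placebo | Placebo | Delayed voxelotor, Total |
| Placebo | Voxelotor only | Yes or no | Placebo | Voxelotor | Total only |
| Placebo | Both | Yes or no | Placebo | No rule given | Total only |
| Voxelotor | Placebo only | Yes | Voxelotor | Placebo | Voxelotor, Total |
| Voxelotor | Both | Yes or no | Voxelotor | No rule given | Voxelotor, Total |

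- Rows 1 and 2 (correct dosing): all rules agree.
- Rows 3 and 5: SAP 2.3.2 contradicts SAP 6 and Protocol 8.1, in opposite directions.
- Rows 4 and 6: the as-treated rule does not say what to do with mixed exposure.
- Rows 3 and 4: the participant is in Total and in neither column, so Voxelotor plus Delayed voxelotor is less than Total.
- Row 5: the participant sits in the open-label Voxelotor column although the first voxelotor dose came in the open-label period.

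**Scale.** Inputs: n = 40 per arm (SAP 2.3.1, the planned size) and illustrative event counts of 4 on voxelotor and 2 on placebo, which are an assumption. As randomized, the risk difference is 4/40 − 2/40 = 10.0% − 5.0% = 5.0 points.

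1. One placebo-randomized participant with an event is moved to voxelotor: 5/41 − 1/39 = 12.2% − 2.6% = 9.6 points, a shift of +4.6. In general the shift is (1 − p_v)/(n + 1) + (1 − p_c)/(n − 1), where p_v and p_c are the as-randomized event proportions on voxelotor and placebo. Here that is 0.90/41 + 0.95/39 = 2.2 + 2.4 = 4.6 points.
2. The same move without an event: 4/41 − 2/39 = 9.8% − 5.1% = 4.6 points, a shift of −0.4.
3. The reverse error, one voxelotor-randomized participant with an event moved to placebo: 3/39 − 3/41 = 7.7% − 7.3% = 0.4 points, a shift of −4.6.

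The shift for the move in step 1 is similar at other event counts: 3/40 against 3/40 goes from 0 to 4/41 − 2/39 = 4.6 points, and 6/40 against 1/40 goes from 12.5 to 7/41 − 0/39 = 17.1 points.

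**The case against.** The strongest reply is that the intended safety rule can be recovered. As-treated grouping is stated in the SAP's analysis section, tied to the safety-evaluable population and repeated in the protocol, and no departure is declared. On that view the word Safety in the SAP 2.3.2 heading is a slip, and the exclusion in Delayed voxelotor is itself as-treated thinking that would send an early-voxelotor placebo participant to the Voxelotor column. This is probably what was meant. It does not settle the matter: SAP 2.3.2 is explicit, SAP 6.6 gives no precedence, and the open-label Voxelotor column still requires randomization to voxelotor, so as written it cannot receive that participant.

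It is also fair to say that efficacy and safety may define Delayed voxelotor differently, since one analysis is by assignment and the other by treatment. That difference is not an error in itself; a distinguishing label would be enough.

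The point that the size is conditional stands in full. Protocol 7.7 defines the wrong-drug error, but neither document reports one.

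**Conclusion.** The plan contradicts itself and the protocol on randomized-period safety grouping, and its open-label safety columns are not exhaustive. Both are worth correcting. The effect is confined to participants whose actual drug differed from the assigned drug, and is zero if there were none. For each such participant, at 40 per arm, the risk difference moves by about 4.6 points if that participant had the event and about 0.4 points if not. These figures rest on the planned arm size and assumed event counts. The study was terminated, so actual arm sizes may differ, and the shift grows roughly as 1/n in smaller arms.

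A reader might infer more than the documents support:

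- *That events drop out of the report.* They do not. They remain in the Total column, and SAP 6.6.1 requires listings of all adverse events, SAEs and deaths.
- *That the wording makes voxelotor look safer.* As-randomized grouping charges events on wrongly given voxelotor to placebo, but it equally charges events on wrongly given placebo to voxelotor. The direction is not fixed.
- *That the open-label gap distorts the placebo comparison.* The open-label safety analysis has no placebo column, so it cannot.
- *That one case would roughly double the difference.* That is a feature of the 4 against 2 example. With 6 against 1, the difference goes from 12.5 to 17.1 points, about 1.4-fold.

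**What to change.** In SAP 2.3.2:

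1. Split the combined randomized-period entry, and limit the as-randomized groups to efficacy.
2. State that randomized-period safety follows the drug actually taken, as in SAP 6 and Protocol 8.1, with one pre-stated convention for mixed exposure. Counting any voxelotor dose as Voxelotor is one option among several. Neither document currently contains a rule.
3. Define the open-label safety columns by the period of the first voxelotor dose, whatever the assigned arm: Voxelotor if in the randomized period, Delayed voxelotor if in the open-label period. The columns are then exhaustive and sum to Total. State which period the Week 12 visit day belongs to, because the efficacy and safety definitions word that boundary differently.
4. Footnote the safety tables with the number of participants whose actual drug differed from the assigned drug, including when it is zero.

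The cost is SAP wording and one derived variable. No new data are needed; Protocol 7.7 already requires medication errors to be recorded in the CRF.
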